5.3.3 Other screening/run-in assessments

5.3.3.1 Serology

Hepatitis B surface antigen, hepatitis C antibody: To be done only at enrolment (Visit 1); test to be performed at central laboratory.

HIV-1 and HIV-2 antibodies: To be done only at enrolment (Visit 1); test to be performed at central laboratory.

Instructions for sample collection, processing, storage, and shipment can be found in the separate laboratory manual provided to the study centers.

5.3.3.2 Serum immunoglobulin E

The levels of total immunoglobulin E (IgE) will be evaluated by a central laboratory. These tests will be performed at Visit 4 (Week 0) (see [Table 3](#)).

Instructions for sample collection, processing, storage, and shipment can be found in the separate laboratory manual provided to the centres.

5.3.4 Pharmacokinetics

5.3.4.1 Collection of samples

For the PK analysis it is important that the date and time of each SC injection is recorded for each patient.

Instructions for sample collection, processing, storage, and shipment can be found in the separate laboratory manual provided to the centers.

Serum will be collected every visit from Visit 4 to Visit 10. On the dosing days, ie, Visit 4, 8 and 9, the serum will be collected as pre-dose.

5.3.4.2 Determination of drug concentration

Samples for determination of drug concentration in serum will be analyzed by a central laboratory on behalf of AstraZeneca, using a validated bioanalytical method. Full details of the analytical method used will be described in bioanalytical report.

5.3.4.3 Storage and destruction of pharmacokinetic samples

The PK samples will be retained at AstraZeneca or designee for a maximum of 3 years following publication of the CSR to properly address potential questions from regulatory authorities (RAs).

A summary of PK analysis results will be reported in the Clinical Study Report (CSR).

5.3.5 Pharmacodynamics

5.3.5.1 Collection of samples

Samples for the analysis of peripheral blood eosinophils will be performed in a central laboratory as part of the routine hematology assessment (complete blood count [CBC]).

5.3.5.2 Immunogenicity

Instructions for immunogenicity (ADA and nAb) sample collection, processing, storage, and shipment can be found in the separate laboratory manual provided to the centers.

The immunogenicity samples will be retained at AstraZeneca or designee for a maximum of 3 years following publication of the CSR to properly address potential questions from RAs.

A summary of the analysis will be presented in the CSR. Details of the analytical method used will be described in a bioanalytical report.

5.3.5.3 Anti-drug antibodies

Serum samples for analysis of anti-drug antibodies (ADA) will be collected pre-dose at selected visits according to the study plan (see [Table 3](#)).

The presence or absence of ADA will be determined in the serum samples using validated bioanalytical methods.

5.3.5.4 Neutralizing antibodies

In vitro neutralizing antibody (nAb) activity is to be tested at all ADA collection time points of Week 16 and later in samples that are ADA-positive. Samples that are ADA-negative will not be tested for nAb.

The presence or absence of neutralizing antibodies will be determined using a validated bioanalytical method.

5.3.6 Pharmacogenetics

Pharmacogenetic samples will not be taken during the study

5.3.7 Biomarker analysis

Samples for biomarker analysis will not be collected during the study.

5.3.8 Handling of biological samples

5.3.8.1 Labelling and shipment of biological samples

The Principal Investigator ensures that samples are labelled and shipped in accordance with the Laboratory Manual and the Biological Substance, Category B Regulations (materials containing or suspected to contain infectious substances that do not meet Category A criteria), see IATA 6.2 Guidance Document'.

Any samples identified as Infectious Category A materials are not shipped and no further samples will be taken from the subject unless agreed with AstraZeneca and appropriate labelling, shipment and containment provisions are approved.

5.3.8.2 Chain of custody of biological samples

A full chain of custody is maintained for all samples throughout their lifecycle.

The Principal Investigator at each center keeps full traceability of collected biological samples from the subjects while in storage at the center until shipment or disposal (where appropriate) and keeps documentation of receipt of arrival (where applicable).

The sample receiver keeps full traceability of the samples while in storage and during use until used or disposed of or until further shipment and keeps documentation of receipt of arrival.

AstraZeneca keeps oversight of the entire life cycle through internal procedures, monitoring of study sites and auditing of external laboratory providers.

Samples retained for further use are registered in the AstraZeneca biobank system during the entire life cycle.

5.4 Additional assessments applicable for the subset of subjects – body plethysmography sub-study

Additional assessments will be performed for a subset of subjects at designated sites, approximately 50 subjects in the study, to determine the effect of benralizumab on the time course of change in lung function as assessed through body plethysmography.

Patients who participate in the sub-study will perform other lung function assessments as mentioned in sections 4.1.1, 4.1.2, 4.1.3, 4.2 and 4.3.

5.4.1 Body plethysmography

Body plethysmography is to be performed only by sites participating in the body plethysmography sub-study and will be performed on approximately 50 patients.

Lung volume subdivisions which include total lung capacity (TLC), residual volume (RV), vital capacity (VC), functional residual capacity (FRC), and inspiratory capacity (IC), as well as airway resistance (Raw and SGaw) measurements, will be performed at study sites by the Investigator or qualified designee according to ATS/ERS guidelines ([Wanger et al 2005](#)) according to the study schedule (see [Table 2](#) and [Table 3](#)).

Lung volumes will be determined by body plethysmography. The test will be performed by qualified pulmonary function technicians with experience performing this assessment. At least 3 FRC values that agree within 5% (ie, the difference between the highest and lowest value divided by the mean is <0.05) should be obtained and the mean value reported.

It is expected that medication restrictions required for spirometry assessments (see section 3.9) are met for body plethysmography too. To enable that, body plethysmography assessments should be done soon after pre-BD spirometry assessments are complete, and before medications are given to patient.

Each site is expected to use their own body boxes to conduct assessments provided they meet the quality and experience criteria set by AstraZeneca. Details related to this procedure are provided in a separate body plethysmography manual provided to the designated study centers.

6. SAFETY REPORTING AND MEDICAL MANAGEMENT

The Principal Investigator is responsible for ensuring that all staff involved in the study are familiar with the content of this section.

6.1 Definition of adverse events

An adverse event (AE) is the development of an undesirable medical condition or the deterioration of a pre-existing medical condition following or during exposure to a pharmaceutical product, whether or not considered causally related to the product. An undesirable medical condition can be symptoms (eg. nausea, chest pain), signs (eg, tachycardia, enlarged liver) or the abnormal results of an investigation (eg, laboratory findings, electrocardiogram). In clinical studies, an AE can include an undesirable medical condition occurring at any time, including run-in or washout periods, even if no study treatment has been administered.

The term AE is used to include both serious and non-serious AEs.

6.2 Definitions of serious adverse event

A serious adverse event (SAE) is an AE occurring during any study phase (ie, run-in, treatment, wash-out, follow-up), that fulfils 1 or more of the following criteria:

- Results in death
- Is immediately life-threatening
- Requires in-patient hospitalization or prolongation of existing hospitalization
- Results in persistent or significant disability/incapacity or substantial disruption of the ability to conduct normal life functions
- Is a congenital abnormality or birth defect
- Is an important medical event that may jeopardize the subject or may require medical intervention to prevent 1 of the outcomes listed above

For further guidance on the definition of a SAE, see [Appendix B](#) to the clinical study protocol (CSP).

6.3 Recording of adverse events

6.3.1 Time period for collection of adverse events

Adverse events will be collected from time of signature of informed consent throughout the treatment period and including the follow-up period (through Day 112 [± 7 days]).

Serious adverse events will be recorded from the time of informed consent.

6.3.2 Follow-up of unresolved adverse events

Any AEs that are unresolved at follow-up in the study are followed up by the Investigator for as long as medically indicated, but without further recording in the case report form (CRF). AstraZeneca retains the right to request additional information for any subject with ongoing AE(s)/SAE(s) at the end of the study, if judged necessary.

6.3.3 Variables

The following variables will be collect for each AE;

- AE (verbatim)
- The date when the AE started and stopped
- Maximum intensity of the AE
- Whether the AE is serious or not
- Investigator causality rating against the Investigational Product (yes or no)
- Action taken with regard to investigational product
- AE caused subject's withdrawal from study (yes or no)
- Outcome.

In addition, the following variables will be collected for SAEs:

- Date AE met criteria for serious AE
- Date Investigator became aware of serious AE
- AE is serious due to
- Date of hospitalization

- Date of discharge
- Probable cause of death
- Date of death
- Autopsy performed
- Causality assessment in relation to Study procedure(s)
- Description of AE

It is important to distinguish between serious and severe AEs. Severity is a measure of intensity whereas seriousness is defined by the criteria in Section 6.2. An AE of severe intensity need not necessarily be considered serious. For example, nausea that persists for several hours may be considered severe nausea, but not a SAE unless it meets the criteria shown in Section 6.2. On the other hand, a stroke that results in only a limited degree of disability may be considered a mild stroke but would be a SAE when it satisfies the criteria shown in Section 6.2.

6.3.4 Causality collection

The Investigator will assess causal relationship between Investigational Product and each Adverse Event, and answer 'yes' or 'no' to the question 'Do you consider that there is a reasonable possibility that the event may have been caused by the investigational product?'

For SAEs causal relationship will also be assessed for other medication and study procedures. Note that for SAEs that could be associated with any study procedure the causal relationship is implied as 'yes'.

A guide to the interpretation of the causality question is found in [Appendix A](#) to the Clinical Study Protocol.

6.3.5 Adverse events based on signs and symptoms

All AEs spontaneously reported by the subject or reported in response to the open question from the study personnel: '*Have you had any health problems since the previous visit/you were last asked?*', or revealed by observation will be collected and recorded in the CRF. When collecting AEs, the recording of diagnoses is preferred (when possible) to recording a list of signs and symptoms. However, if a diagnosis is known and there are other signs or symptoms that are not generally part of the diagnosis, the diagnosis and each sign or symptom will be recorded separately.

6.3.6 Adverse events based on examinations and tests

The results from protocol mandated laboratory tests and vital signs will be summarized in the clinical study report. Deterioration as compared to baseline in protocol-mandated laboratory

values, vital signs should therefore only be reported as AEs if they fulfil any of the SAE criteria or are the reason for discontinuation of treatment with the investigational product.

If deterioration in a laboratory value/vital sign is associated with clinical signs and symptoms, the sign or symptom will be reported as an AE and the associated laboratory result/vital sign will be considered as additional information. Wherever possible the reporting Investigator uses the clinical, rather than the laboratory term (eg, anaemia versus low haemoglobin value). In the absence of clinical signs or symptoms, clinically relevant deteriorations in non-mandated parameters should be reported as AE(s).

Any new or aggravated clinically relevant abnormal medical finding at a physical examination as compared with the baseline assessment will be reported as an AE.

6.3.6.1 Symptoms of the disease under study

6.3.7 Hy's Law

Cases where a subject shows elevations in liver biochemistry may require further evaluation and occurrences of AST or ALT $\geq 3 \times \text{ULN}$ together with total bilirubin $\geq 2 \times \text{ULN}$ may need to be reported as SAEs. Please refer to [Appendix D](#) for further instruction on cases of increases in liver biochemistry and evaluation of Hy's Law.

6.3.8 Disease progression

When collecting AEs, the recording of diagnoses is preferred, when possible, to recording a list of signs and symptoms. Asthma symptoms or signs, such as wheeze, cough, chest tightness, dyspnea, breathlessness and phlegm, will be recorded as AEs only when:

- The sign or symptom is serious according to definitions, see Section [6.1](#)
- The patient discontinues the study due to the sign or symptom
- The sign or symptom is new to the patient or not consistent with the patient's pre-existing asthma history (defined as within 1 year of Visit 1) as judged by the Investigator.

Asthma exacerbation should be recorded as an AE or SAE only if it fulfills any of the above criteria.

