5.2.2.2 Brief physical examination

The brief physical examination includes an assessment of the general appearance, abdomen, cardiovascular, and respiratory system. For the brief physical examination only information on whether the assessment was performed or not is to be recorded.

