5.2.4 Vital signs

5.2.4.1 Pulse and blood pressure

Pre-dose vital signs (pulse, blood pressure, respiration rate, and body temperature) are to be obtained in accordance with schedule provided in [Table 2](#) and [Table 3](#)

Vital signs are to be taken prior to IP administration, and, if possible, before blood drawing and usual asthma controller medication. Vital signs should also be taken prior to bronchodilator administration if applicable for that visit.

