6.7 Management of investigational product-related reactions

Appropriate drugs (eg, epinephrine, H1 and H2 antihistamines, and corticosteroids), and medical equipment to treat acute anaphylactic reactions must be immediately available. Study personnel must be trained to recognize and treat anaphylaxis (Lieberman et al 2010). Details on anaphylaxis management are provided in Appendix F.

Anaphylaxis will be defined as a serious reaction that is rapid in onset and may cause death (Simpson et al 2006). Anaphylaxis typically manifests as 1 of 3 clinical scenarios:

1. The acute onset of a reaction (minutes to hours) with involvement of the skin, mucosal tissue, or both, and at least 1 of the following: a) respiratory compromise or b) reduced blood pressure or symptoms of end-organ dysfunction
2. Two or more of the following that occur rapidly after exposure: involvement of the skin/mucosal tissue, respiratory compromise, reduced blood pressure or associated symptoms and/or persistent gastrointestinal symptoms
3. Reduced blood pressure after exposure

Patients will have had a pre-assessment (ie, vital signs and lung function) prior to IP administration) and should be observed after IP administration for a minimum of 2 hours for the appearance of any acute drug reactions.

In order to help understand the potential drug-relatedness of any acute reaction, a blood sample should be drawn during the event for possible additional ADA testing (if not already scheduled for this visit). Serum tryptase or other blood or urine testing relevant to the diagnosis of anaphylaxis may be obtained at a local lab at the discretion of the Investigator.

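### Protocol 6.3.8 does not make suspected relation to the investigational product a reason to record an asthma-type symptom as an AE

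*Protocol*

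**What the plan says.** Protocol 6.3.8 sets a specific rule for the disease under study: "Asthma symptoms or signs, such as wheeze, cough, chest tightness, dyspnea, breathlessness and phlegm, will be recorded as AEs only when" at least one of three conditions is met. The first is seriousness. The second is that the patient leaves the study because of the event. The third begins "The sign or symptom is new to the patient or not consistent with" and refers to the patient's asthma history over the year before Visit 1, as the Investigator judges it. The section then applies the same conditions to asthma exacerbations. It also prefers a diagnosis to a list of symptoms.

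Other sections bear on the same events:

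- **6.1 and 6.3.5** define and collect AEs broadly, including worsening of an existing condition, whatever its cause.
- **6.3.4** asks for a yes/no causality rating on each AE.
- **6.3.6** makes an AE of "Any new or aggravated clinically relevant abnormal medical finding at a physical examination", and adds: "If deterioration in a laboratory value/vital sign is associated with clinical signs and symptoms, the sign or symptom will be reported as an AE". Section 5.2.2 likewise has clinically significant new or aggravated findings reported as AEs.
- **6.7** says that patients "should be observed after IP administration for a minimum of 2 hours for the appearance of any acute drug reactions".
- **SAP 4.2.9.1** tabulates AEs by system organ class and preferred term, by causality and intensity, and through a hypersensitivity query. All of these start from recorded AEs.

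**The concern.** Bronchospasm, wheeze and dyspnea can be asthma, and they can also be signs of a reaction to an injected antibody. Protocol 1.4 names hypersensitivity as a theoretical risk of anti-drug antibodies, and Appendix D lists wheeze and dyspnea as respiratory compromise in its anaphylaxis criteria. In this population the third condition of 6.3.8 filters strongly. Patients enter with at least two steroid-treated exacerbations in the past year and ACQ-6 of 1.5 or more (3.1). They must also have recent symptoms, rescue use or night waking at randomization (3.3.1). Wheeze or cough will seldom be new to them.

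An Investigator may therefore see a mild symptom, suspect the injection, and find nothing in 6.3.8 that calls for a record. Without a record there is no causality rating, and the event cannot reach the AE or hypersensitivity tables. Safety and tolerability is a stated objective with AEs as an outcome measure (2.3), so a rule that can leave out a suspected drug reaction deserves a second look even when the event is mild.

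**Working it through.** This is a check of rules, and the plan gives no figure to reproduce. The test case is a mild, non-serious cough or chest tightness that resembles the patient's usual asthma. The patient stays in the study, and the Investigator thinks IP may have caused it. Each possible route to an AE record is taken in turn.

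1. **Condition 1 of 6.3.8 (serious).** Not met, by construction. Section 6.7 defines anaphylaxis as serious, and Appendix A gives intensively treated allergic bronchospasm as an example of an important medical event. Both are captured and lie outside this point.
2. **Condition 2 (leaves the study).** Not met. The condition names the study, not IP.
3. **Condition 3 (new or inconsistent with history).** Open to the Investigator, who may regard an abrupt post-dose onset as inconsistent. Nothing requires that judgement.
4. **Reaction diagnosis.** Also open, and encouraged by the preference for diagnoses. It is not required.
5. **General rules in 6.1 and 6.3.5.** Broad enough to cover the event, but 6.3.8 is the specific rule for asthma symptoms and its wording is exclusive.
6. **Causality rating in 6.3.4.** Applies once an AE exists. It does not create one.
7. **Examination finding (5.2.2, 6.3.6).** Captures, for instance, a clinically significant wheeze on examination. It does not reach cough or chest tightness without a finding, and no examination is timed after the injection.
8. **Vital-sign or laboratory deterioration (6.3.6).** Captures a symptom that accompanies one. The scheduled measurements do not help here: "Vital signs are to be taken prior to IP administration".
9. **Blood sample for anti-drug antibodies (6.7) or concomitant medication (7.7).** May leave a trace, but neither is an AE record with a causality rating.
10. **The heading "6.3.6.1 Symptoms of the disease under study".** No text stands beneath it in the copy reviewed. It may have been lost in extraction, so it counts neither way.

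Result: routes 3 and 4 depend on the Investigator's choice, routes 7 and 8 need an accompanying finding, and no route makes suspicion of IP itself a reason to record.

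**Size.** The documents give no rate, so the range below is assumed.

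- Planned benralizumab doses: 115 patients × 3 = 345.
- At 0.1% of injections causing a mild asthma-type symptom: 345 × 0.001 = 0.345.
- At 0.5%: 345 × 0.005 = 1.725.
- At 1%: 345 × 0.01 = 3.45.

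These are drug-caused symptoms that would occur. They are ceilings on what 6.3.8 could drop, because the routes above catch some. The share that would go unrecorded cannot be estimated from the documents.

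**The case against.** The strongest reply is that the case nearly cancels itself. It needs an Investigator who suspects IP, still calls the symptom consistent with the patient's asthma, and also declines to record a reaction diagnosis. The same person makes all three judgements, and real suspicion will usually lead to condition 3 or to a diagnosis. This stands, and it is why the gap is small. It does not close the gap, because the text leaves the result to how each Investigator reads condition 3.

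A second reply is that keeping habitual disease symptoms out of AE data is deliberate and sensible, since asthma status is measured by ACQ-6 and the global impression scales. This stands too. The remedy should not undo it.

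A third concerns 5.2.2.2: "For the brief physical examination only information on whether the assessment was performed or not is to be recorded". A reader might infer that findings at a brief examination are lost. The documents do not support that. The sentence limits what the examination form holds, while 5.2.2 and 6.3.6 still require a clinically significant finding to be reported as an AE.

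A reader might also infer that every asthma-type symptom starting in the 2-hour observation should become an AE automatically. That does not follow. Patients are symptomatic by inclusion, and their morning controller therapy is withheld until spirometry is done (5.1.1), so symptoms on dosing days are expected. With 230 × 3 = 690 dosing visits and an assumed 1% to 10% affected, such a rule would add about 7 to 69 records, mostly background asthma.

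**Conclusion.** The point holds in a narrow form. Under 6.3.8 as written, a mild, non-serious asthma-type symptom or exacerbation that looks like the patient's usual disease need not be recorded even when the Investigator suspects IP. The exceptions are the discretionary and finding-based routes set out above. This rests on reading 6.3.8 as the governing rule for asthma symptoms; any missing text under 6.3.6.1 could change that.

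The number of affected events is unknown and probably very small. The assumed rates bound drug-caused symptoms and do not measure unrecorded ones.

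The documents do not support a reading that the trial misses serious reactions, anaphylaxis or diagnosed hypersensitivity, all of which are captured. Nor do they support a reading that 6.3.8 favours one arm by design: it is applied blind and identically in both. The primary endpoint, pre-bronchodilator FEV₁, does not depend on AE recording. The label is a cheap improvement of minor severity.

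**What to change.** Add one bullet to Protocol 6.3.8: *The Investigator considers there is a reasonable possibility that the sign or symptom was caused by the investigational product.* It uses the standard of the existing causality question in 6.3.4, so it needs no new judgement and no new CRF field. Because 6.3.8 ties exacerbations to the same conditions, the bullet covers them as well.

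Count these events in the ordinary AE tables of SAP 4.2.9.1, including those by causality and the hypersensitivity summary. A separate listing in place of those tables would keep related events out of the place where readers look for them. No automatic 2-hour trigger or onset-time field is needed.

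The cost is one sentence, handled under the change process in Protocol 10.5, and a few extra non-serious AE records in both arms, since suspicion is formed blind. Habitual asthma symptoms stay out, because Appendix A already classes deterioration from lack of effect as not a reasonable possibility of relation.

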3.10.1 Procedures for discontinuation of a subject from investigational product

At any time, subjects are free to discontinue investigational product or withdraw from the study (ie, investigational product and assessments – see Section 3.11), without prejudice to further treatment. A subject that decides to discontinue investigational should always be asked about the reason(s) and the presence of any adverse events.

All patients must be administered the first dose of IP. If the patient misses the first IP administration they must be discontinued from the study and should return for IPD visit. If the patient receives the first IP administration but misses both the 2nd and the 3rd dose they must be discontinued from the study and should return for the IPD visit. If the patient receives the first IP administration but misses either the 2nd or 3rd dose they need not discontinue from the study

All patients who prematurely discontinue investigational product should return to the study center and complete the procedures described for the premature IP Discontinuation (IPD) visit within 4 weeks \pm 3 days after the last dose of IP. At that visit, although no longer on IP, patients should be encouraged to remain in the study to complete all subsequent study visits, procedures, and assessments. Note that in this case, the IPD visit replaces the nearest regular visit while the following visits continue as possible

If the patient is not willing to participate further in the study after the IPD visit, the patient should still return for a follow up visit 8 weeks \pm 3 days after the last dose of IP for final study-related assessments.

The reasons for premature discontinuation of IP should be recorded in the eCRF.

¹ Patient is considered lost to follow up when any of the following attempts of contact are failed: 3 attempts of either phone calls, faxes or emails; having sent 1 registered letter/certified mail; or 1 unsuccessful effort to check the vital status of the patient using publicly available sources, if allowed by local regulations.

If a subject is withdrawn from study, see Section 3.11.

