##### **4.2.9.1 Adverse events**

Adverse events (AEs) will be summarized for the on-study period, as defined in Section 3.5.1. All summaries will be presented by treatment group.

An overall summary table will be produced showing the number and percentage of patients with at least 1 AE in any of the following categories: AEs, serious adverse events (SAEs), AEs with outcome of death, and AEs leading to discontinuation of IP (DAEs). The total number of AEs in the different AE categories in terms of AE counts will also be presented (ie, accounting for multiple occurrences of the same event in a patient).

Adverse events, AEs with outcome of death, and SAEs will be summarized by SOC and PT assigned to the event by MedDRA. For each PT, the number and percentage of patients reporting at least 1 occurrence will be presented (ie, multiple occurrences of an AE for a patient will only be counted once). Adverse events causing discontinuation of the study treatment and SAEs causing discontinuation from the study will also be summarized.

The rate of AEs per person-years at risk, calculated as (number of patients reporting AE)/(total period with patients at risk for AE), will also be reported. The total period at risk for each patient will be defined as the period from first dose of study treatment to the follow-up visit (Week 16). Rates will be expressed in terms of events per 100 patient-years.

A summary of the most common (frequency of  $\geq 5\%$ ) AEs will be presented by PT. Adverse events will be summarized by PT and Investigator's causality assessment (related versus not related) and maximum intensity. If a patient reports multiple occurrences of the same AE within the same study period, the maximum intensity will be taken as the highest recorded maximum intensity (the order being mild, moderate, and severe). Adverse events of injection site reactions (high-level term of administration and injection site) and hypersensitivity (standardized MedDRA query of hypersensitivity) will be summarized by PT. The summary of injection site reactions will be summarized by injection site location and number of IP administrations.

Adverse events related to device malfunction will be listed. All adverse events will be listed.

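### Non-serious asthma worsening consistent with the patient's history is an AE only if the patient leaves the study, so one that ends only investigational product is missing from the SAP's count of AEs leading to IP discontinuation

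*Protocol*

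**What the plan says.** Protocol 6.3.8 gives three alternative conditions under which asthma signs or symptoms are recorded as AEs:

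- "The sign or symptom is serious according to definitions";
- "The patient discontinues the study due to the sign or symptom";
- it is novel for that person or out of keeping with their known asthma, looking back one year from Visit 1, as judged by the Investigator.

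Exacerbations follow the same rule: "Asthma exacerbation should be recorded as an AE or SAE only if it fulfills any of the above criteria".

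Elsewhere the documents keep stopping IP apart from leaving the study. Protocol 3.10.1 says "At any time, subjects are free to discontinue investigational product or withdraw from the study", and of those who stop IP it says "patients should be encouraged to remain in the study to complete all subsequent study visits, procedures, and assessments". Protocol 6.3.3 has one AE field for the action taken with IP and another for whether the AE caused withdrawal from the study. Protocol 6.3.6, the corresponding rule for laboratory values and vital signs, makes deteriorations reportable if they are serious or "are the reason for discontinuation of treatment with the investigational product". The overall safety table in SAP 4.2.9.1 counts patients with "AEs leading to discontinuation of IP (DAEs".

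**The concern.** The recording rule and the table it feeds use different events. 6.3.8 asks whether the patient left the study; the SAP row asks whether IP was stopped. Two patients could stop IP for the same non-serious, familiar worsening. The one who then leaves the study has an AE and is counted; the one who stays has none and is not. Whether a stop is counted then depends on retention rather than on why dosing ended.

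The restriction in 6.3.6 rests on laboratory and vital-sign results being summarized anyway. Asthma exacerbations have no such backstop. They are not a listed outcome in the protocol or SAP objectives, and the SAP plans no summary of on-study exacerbations. At stake is how one descriptive safety row is read.

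**Working it through.** No sample size, power or event count enters this point. The check is a reading of the rules against each other, with a count of logical cases.

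**Step 1: which cases are lost.** Take a patient who stops IP because of asthma worsening and stays in the study. The study-discontinuation condition is not met, so only seriousness and novelty matter. Two yes/no attributes give 2 × 2 = 4 cases under 6.3.8:

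| Serious? | New or inconsistent with history? | Recorded as an AE? | Can enter the IP-discontinuation row? |
|---|---|---|---|
| Yes | Yes | Yes | Yes |
| Yes | No | Yes | Yes |
| No | Yes | Yes | Yes |
| No | No | No | No |

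Three of the four cases are captured and one is lost. These are logical cases, not frequencies.

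**Step 2: why the lost case cannot be recovered in the AE data.** The field for action taken with IP (Protocol 6.3.3) is part of an AE record. With no AE record, nothing can be flagged as leading to IP discontinuation.

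**Step 3: when it can happen.** Doses are planned for Days 0, 28 and 56. By the missed-dose rule in Protocol 3.10.1:

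- Stop after dose 1: doses 2 and 3 are both missed (two doses). The patient must be discontinued from the study and may then meet the second condition of 6.3.8.
- Stop after dose 2: one dose is missed. The patient need not leave, so the gap is open.
- After dose 3: no planned dose remains to be stopped.

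The clear window therefore runs between doses 2 and 3, planned as 56 − 28 = 28 days. Stops after dose 1 are uncertain, because the same section also encourages all patients who stop IP to stay.

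**Step 4: what remains visible.** Protocol 3.10.1 requires the reason for stopping IP in the eCRF. SAP 4.2.1 tabulates IP discontinuation with reason by arm and shows separately those who stopped IP but completed follow-up. SAP 8.1 adds tables of discontinuation reasons. The stop is therefore reported, though not as an AE.

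**The case against.** The strongest reply is that the gap is narrow and the information survives. Serious or atypical worsening is captured whether or not the patient stays. The only asthma-specific reason for stopping IP listed in Protocol 3.10 is an event requiring mechanical ventilation, which would be expected to qualify as serious. Protocol 7.2 has an acute or emerging exacerbation lead to a rescheduled dose rather than an end to dosing. The disposition table shows the stops. All of this stands, and it limits the point to one row of one table.

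It can also be said that restricting AE recording for the disease under study is deliberate, and that Appendix A rates deterioration from lack of effect as not causally related. The restriction is a legitimate choice, but it does not explain why the trigger is the study here and IP in 6.3.6. The SAP row is also not limited to related events. Protocol 8.5.2.3 does plan a summary of AEs leading to study discontinuation, which fits the 6.3.8 trigger, but the SAP row on IP still does not.

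Protocol 5.2.2 and 6.3.6 make new or aggravated relevant physical findings reportable as AEs. That might bring in some cases, but how it sits with the restrictive wording of 6.3.8 is not stated.

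A reader might infer that, because entry requires at least 2 exacerbations in the prior year, any later one is consistent with history. The documents do not say so; 6.3.8 leaves it to the Investigator, case by case.

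**Conclusion.** The mismatch is real. Applied exactly, 6.3.8 omits from the SAP's IP-discontinuation row a non-serious, history-consistent worsening that ends IP while the patient remains, most clearly between doses 2 and 3. The effect is confined to descriptive safety output. The primary FEV1 analysis and the sample size do not depend on it.

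Three stronger readings are tempting and not supported:

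- That asthma worsening counts as an AE only when the patient leaves the study. Two other conditions apply regardless of staying.
- That the row could be halved or the comparison between arms reversed. The documents give no rate. An assumed 1% to 3% of 115 per arm would be 1.15 to 3.45 patients, but nothing supports that range, and it is not confined to the window between doses 2 and 3. Neither the size of the row nor any difference in loss between arms can be derived.
- That the Kaplan-Meier split by treatment-related reason in SAP 8.1 is distorted. For the dropout-based imputation, that appendix sends patient decision and other reasons to review before unblinding, so a label other than adverse event does not settle the classification.

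The conclusion assumes that sites follow 6.3.8 literally and that no eCRF instruction outside these documents already covers the case.

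**What to change.** In the second bullet of Protocol 6.3.8, make the condition discontinuation of investigational product or of the study because of the sign or symptom. This matches 6.3.6 and the SAP row, and leaves the other two conditions as they are. Carry the change into the eCRF completion guideline. The cost is a one-phrase amendment, a few more AE records and a slightly higher count of AEs leading to IP discontinuation.

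Separately, reconcile the sentences in Protocol 3.10.1 that require study discontinuation after doses 2 and 3 are both missed with those encouraging all patients off IP to remain, so that it is clear which patients can stop IP and stay.

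If the protocol is not amended, footnote the SAP row to say which asthma events it cannot contain, and cross-tabulate it with the disposition reasons for stopping IP. That needs no new data.
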